The Impact of Training with Whole Body EMS

NCT04288154

4/20/2022

The Impact of Training with Whole Body-EMS

Version6 : April 20, 2022

Aims and Objectives

This study will be undertaken in healthy adults who are employees at Mayo Clinic, Rochester MN

Primary Aim:

To assess the impact of training with whole body-EMS for a 16-week period of time, involving 1.0 x 20 minute training sessions per week, on peripheral endothelial function as measured using EndoPAT.

Secondary Aims:

To assess the impact of training with whole body-EMS for a 16-week period of time, involving 1.0 x 20 minute training sessions per week, on:

- i) Body mass index, waist circumference, percentage body fat and distribution, and blood pressure
- ii) Serum lipid profile, blood glucose and HbA1c, blood inflammatory markers including high sensitivity-CRP and uric acid, and novel cardiovascular markers in the blood such as fibrinogen, homocysteine and lipoprotein
- iii) VO₂ maximum (Cardiopulmonary exercise testing parameters)
- iv) Maximum strength and maximum power in chest press and leg press

- v) Symptoms of angina as measured by the Rose Questionnaire
- vi) Quality of life as measured by the LASA Questionnaire, symptoms of depression as measured by the PHQ-9 Questionnaire, and symptoms of stress as measured on the Perceived Stress Scale
- vii) Temporal changes in blood levels of creatinine kinase

Sensorimotor characteristics (visual-motor reaction time, peak knee muscular force, muscular force steadiness, and balance/posture)

Hypotheses

We hypothesize that healthy adults who are employees at Mayo Clinic, Rochester MN who undergo whole body-EMS training for a 16-week period of time, involving 1.0 x 20 minute training sessions per week, will experience:

- i) A significant improvement in peripheral endothelial function measured using EndoPAT
- ii) A significant improvement in body mass index, waist circumference, percentage body fat and distribution, and blood pressure
- iii) A significant improvement in lipid profile, blood glucose and HbA1c, blood inflammatory markers including high sensitivity-CRP and uric acid, and novel cardiovascular markers in the blood such as fibrinogen, homocysteine and lipoprotein
- iv) A significant improvement in VO₂ maximum and cardiopulmonary exercise testing parameters

- v) A significant improvement in maximum strength and maximum power in chest press and leg press

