- vi) A significant improvement in symptoms of angina as measured by the Rose Questionnaire
- vii) A significant improvement in quality of life as measured by the LASA Questionnaire, symptoms of depression as measured by the PHQ-9 Questionnaire, and symptoms of stress as measured on the Perceived Stress Scale
- viii) No significant difference in blood levels of creatinine kinase across time
- viii) A significant improvement in sensorimotor characteristics (visual-motor reaction time, peak knee muscular force, muscular force steadiness, standing balance, and overhead squatting posture)
- ix)

Methods

Trial Design

This study will consist of a **blinded randomized controlled prospective study design**, and will include 80 healthy individuals who are employees at Mayo Clinic, Rochester MN.

Excluded subjects will consist of:

- Subjects under the age of 18
- Pregnancy/or suspected pregnancy
- Subjects with a history of liver or kidney disease, acute illness, taking medications (such as glucocorticoids)
- Subjects who have conditions (such as chronic inflammatory muscular diseases or Cushing's syndrome) that affect muscle mass

- Individuals with pacemakers and implantable cardiac defibrillators
- Individuals who conduct any other type of resistance training (> 45 minutes/week)
- Individuals who have regular “high” alcohol consumption (> 80g/day on 5 days a week), or are under acute influence of alcohol, drugs narcotics, and/or painkillers
- Subjects unable to consent to or participate in the 16-week EMS intervention or be available for follow up (1).
- Subjects who report recent surgeries
- Cardiac arrhythmias
- Active medical implants
- Epilepsy
- Seizures
- Severe circulatory disorders
- Arterial circulatory disorders
- Strong bleeding tendencies (hemophilia)
- Bleeding
- Abdominal wall hernia
- Inguinal hernia
- Tuberculosis
- Tumor diseases
- Arteriosclerosis in advanced stage
- Severe neurological disorders
- Diabetes mellitus
- Febrile diseases
- Acute bacterial or viral infections
- Liver diseases
- Kidney diseases
- Cardiovascular diseases
- Coronary heart diseases
- Infected or wounded areas of the skin
- Skin cancer
- Rhabdomyolysis

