whole body-EMS machine. Individuals will be trained in a ratio of 2 subjects to 2 machines and one trainer. Subjects in the control group will undergo training with a similar physical exercise program as those in the interventional group undertaking routine exercise maneuvers (including squatting, lunging, forward flexion etc.), and will use the same equipment and will be ‘dressed’ as if they were undergoing whole body-EMS, but will have no/subthreshold electricity signals applied to their body vest. The EMS machine will be switched on and show normal wave patterns suggesting that it is working normally, but study participants will be blinded to whether or not they are receiving percutaneous electrical stimulation while doing the routine exercise maneuvers. This will be applied for a 16-week training program 1.0 time a week for a maximum of 20 minutes per session, with no intermittent breaks. Individuals will be trained in a ratio of 2 subjects to 2 machines and one trainer. Individuals will be randomized to each group, and they and the study investigators will be blinded to the intervention. Otherwise, individuals in both groups will be asked to maintain their normal lifestyles.

In order to generate a safe, individualized, joint-friendly, and time-efficient exercise protocol which will be potentially effective and feasible for a cohort that may have physical limitations, we plan to implement the same previously utilized whole body-EMS training protocol successfully applied in other whole body-EMS trials undertaken in Germany that have focused on body composition and functional parameters (1-4). Briefly, with the whole body-EMS equipment (miha bodytec®, Gersthofen, Germany) we will apply a simultaneous but region specific stimulation of all the main muscle groups with an overall area of up to 2750 cm². We will consistently run an guided whole body-EMS program in groups who will always supervised

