and guided by two certified instructor (i.e., two applicants coached by one instructor). Whole body-EMS will be conducted on approximately the same day, once a week (i.e., $1.0 \times \text{week}$) for 20 minutes. The device will apply a bipolar electric current; we will select an impulse frequency of 85 Hz, an impulse width of 350 μs , and will apply an interval approach with 4 seconds of stimulation alternating with 4 seconds of rest. Gentle slight dynamic exercises will be performed during the 4-second stimulation phase. Each session will consist of 10–14 dynamic exercises structured in one to two sets of eight repetitions performed without any additional weights in a standing position. Most exercises will be based on a low amplitude squat exercise ($< 35^\circ$ leg flexion) with full amplitude movements of the arms (such as rowing, lat pulley, or butterfly). The emphasis of the protocol however will not be the effect on muscles induced by voluntary activation but by the application of whole body-EMS with high current intensity during functional movements. During the course of the study, the instructor will progressively increase the volume of stimulation by extending the length of the session from 14 up to 20 minutes after 4 weeks of training. The intensity of the stimulation will be regulated using a rate of perceived exertion (RPE) scale to generate a sufficient, but tolerable, intensity of EMS application to all stimulated areas. For each of the muscle groups stimulated, participants will be encouraged to exercise at a RPE of “6–7 out of 10” (i.e., “hard+ to very hard”) on the Borg CR10 Scale (5). This specification will be achieved in close interaction between the participant and instructor. Based on initial start settings determined after 4, 8, and 12 weeks, the impulse intensity will be increased slightly every 3 minutes to maintain/slightly increase the prescribed RPE during each session (**refer to Supplemental Video**).

Schedule of events

| | Baseline Day 0 | Weeks 1-7 | Week 8 follow-up (+/- 7 days) | Weeks 9-15 | Week 16 follow-up (+/-7 days) |
|---|----------------|-----------|-------------------------------|------------|-------------------------------|
| Informed Consent | X | | | | |
| Brief review of medical history | X | | | | |
| Exercise with EMS device | X | X | X | X | X |
| Blood draw and laboratory testing** | X | | | | X |
| Creatinine Kinase | X | | X | | X |
| Physical Assessment* | X | | | | X |

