This will be a randomized controlled trial in which there will be an interventional group and a control group into which individuals will be randomly assigned in a 1:1 ratio. We will match individuals, a priori, as best as possible on age (within 5 years) and sex. Baseline, demographic and risk factor distribution will be outlined in Table 1 of our analyses. The following parameters will be measured in all subjects at baseline, and at 16-weeks follow-up (immediately after completing training in either study protocol depending on which group the participant is in): peripheral endothelial function measured with RH-PAT using EndoPAT; body weight and body mass index; waist circumference; blood pressure; total cholesterol, low and high density

lipoprotein cholesterol and triglycerides, fasting blood glucose and HbA1c; high sensitivity-CRP, uric acid, fibrinogen, homocysteine and lipoprotein A; percentage body fat; maximum strength and maximum power in leg press; VO₂ maximum, maximal heart rate, and scores measured on the Rose questionnaire, LASA questionnaire, PHQ-9 questionnaire and Perceived Stress Scale. In addition, serum creatinine kinase will be measured at baseline, 8 weeks and 16 weeks.

We will compare values of each parameter between groups at baseline and after 16-weeks using unmatched analyses (using Student's t-test when comparing the aforementioned measures as continuous variable and using Chi-squared test when characterizing variables in categories of normal vs. abnormal). We will also assess for differences in the value of each parameter within groups between baseline and 16-weeks follow-up using matched analyses (using Student's paired t-test when comparing the aforementioned measures as continuous variable and McNemar's test when characterizing variables in categories of normal vs. abnormal). Lastly, we will compare the differences between baseline and 16-weeks follow-up for each parameter between groups using unmatched analyses (using the student t-test when comparing the aforementioned measures as continuous variable and using Chi-squared test when characterizing variables in categories of normal vs. abnormal).

Clinical Significance

Cardiovascular disease (CVD) is the primary cause for morbidity, mortality, and the associated rising health care costs in the world (21). According to 2012 statistics, poor diet, smoking, and

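### Hypothesis i names no comparator and none of the three planned RH-PAT comparisons decides the primary aim, so a pre-post gain in the EMS arm alone could be read as success

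*Combined protocol and SAP*

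**What the plan says.** The Hypotheses section predicts, for healthy adults "who undergo whole body-EMS training for a 16-week period of time", the following: "A significant improvement in peripheral endothelial function measured using EndoPAT". Neither that sentence nor the Primary Aim mentions the control group.

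The Statistical Analysis section applies three kinds of comparison to every parameter, RH-PAT included:

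1. Between arms at each time point: "We will compare values of each parameter between groups at baseline and after 16-weeks using unmatched analyses".
2. Within each arm: "We will also assess for differences in the value of each parameter within groups between baseline and 16-weeks follow-up using matched analyses".
3. Between arms in change: "Lastly, we will compare the differences between baseline and 16-weeks follow-up for each parameter between groups using unmatched analyses".

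Each also has a version on normal/abnormal categories; for RH-PAT the cut-off is 1.7 (Outcomes and Measurements). The section gives no ranking, primary test, significance level or success criterion.

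The Intervention section describes an active sham: "Subjects in the control group will undergo training with a similar physical exercise program as those in the interventional group undertaking routine exercise maneuvers", with the same equipment and no or subthreshold current.

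**The concern.** The trial is randomised so that the effect of stimulation can be separated from everything else that happens over 16 weeks. Only a between-arm comparison does that. A paired test in the EMS arm asks whether RH-PAT changed among people who had stimulation, exercise and 16 weeks of trial participation together. The sham arm has all of these except effective stimulation, so a paired gain cannot be credited to EMS.

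As worded, hypothesis i is satisfied by that paired gain. It could also be claimed from a result that is significant in the EMS arm but not in the sham arm, which is not a test of the difference between arms either.

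The protocol's own table of previous studies shows both patterns. In the trial of EMS against high-intensity resistance exercise, lean mass and leg strength rose significantly in both arms with no significant group difference (p = .395 and p = .215). In the heart-failure trial, ejection fraction is reported as p = 0.003 in one arm and p = 0.18 in the other, with no between-arm p-value shown.

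Separately, choosing among three unranked tests after seeing the data raises the chance of a false favourable result above that of any single test.

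**Working it through.** The plan gives no alpha, effect size, SD or power, so there is no figure to reproduce. The check illustrates the size of the problem.

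**Inputs from the documents.** 80 participants (Trial Design) randomised 1:1 (Intervention), hence 40 per arm, taken here with no dropout.

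**Assumptions.** Each test is two-sided at 0.05, so 2.5% falls in the direction favouring EMS. EMS adds nothing over sham. Both arms share a gain *g*, in SD of RH-PAT. The baseline to 16-week correlation is ρ = 0.3, 0.5 or 0.7, with equal SDs at both visits.

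**Step 1. EMS-arm paired test.** The SD of change is √(2(1−ρ)), so the standardised change is dz = g/√(2(1−ρ)). The chance of a favourable result is P(T > 2.023), where T is noncentral t with 39 degrees of freedom and noncentrality dz√40.

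Example with g = 0.2 and ρ = 0.5: dz = 0.2/√1 = 0.2; noncentrality = 0.2 × 6.325 = 1.265; probability = 0.234.

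**Step 2. EMS arm favourably significant, sham arm not.** The arms are independent and have the same probability p, so this is p(1−p). In the example, 0.234 × 0.766 = 0.179.

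| Shared gain g | Paired test favourable, ρ = 0.3 / 0.5 / 0.7 | EMS significant, sham not |
|---|---|---|
| 0 | 2.5% throughout | about 2.4% |
| 0.1 SD | 7.5 / 9.0 / 12.2% | 7.0 / 8.2 / 10.7% |
| 0.2 SD | 18.0 / 23.4 / 35.7% | 14.7 / 17.9 / 23.0% |
| 0.3 SD | 34.6 / 45.7 / 66.6% | 22.6 / 24.8 / 22.2% |

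The paired-test rates are power against a real shared change, not type I error. They show how often the paired test would be misread as an EMS effect.

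**Step 3. Between-arm change test.** A shared gain cancels in the difference between arms. In simulation the favourable rate was 2.4 to 2.6% for every g from 0 to 0.3 SD.

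**Step 4. Choosing among three tests when nothing changes in either arm.** The 16-week t-test, the change t-test and the EMS-arm paired t-test were simulated together. At least one is significant in about 12% of trials counting both directions, and favours EMS in about 6%, against 2.5% for one designated test. The two between-arm tests alone give about 4.4 to 4.8% favourable; adding the paired test brings it to about 6%.

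**Step 5. What the designated test can detect.** A two-sample t-test with 40 per arm has 80% power at a standardised difference of 0.634.

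| ρ | Change test: 0.634 × √(2(1−ρ)) | Baseline-adjusted: 0.634 × √(1−ρ²) |
|---|---|---|
| 0.3 | 0.634 × 1.183 = 0.75 SD | 0.634 × 0.954 = 0.61 SD |
| 0.5 | 0.634 × 1.000 = 0.63 SD | 0.634 × 0.866 = 0.55 SD |
| 0.7 | 0.634 × 0.775 = 0.49 SD | 0.634 × 0.714 = 0.45 SD |

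Both columns are in SD of RH-PAT. The adjusted column ignores the one degree of freedom spent on the covariate.

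**The case against.** The strongest reply is that the valid test is already planned. The protocol calls the study randomised, controlled and blinded, describes a sham arm, and lists between-arm comparisons both first and last. Nothing says a within-arm p-value will support an efficacy claim, so only a label is missing. That is fair as to how easy the repair is. It does not remove the gap: no sentence ties hypothesis i to a between-arm test, and two such tests (16-week value and change) stand unranked.

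Second, the large rates need a shared gain that no document supplies, and the protocol suggests it may be small. Training is once a week for at most 20 minutes ("Gentle slight dynamic exercises will be performed during the 4-second stimulation phase"), and the section on exercise and endothelial dysfunction describes a study suggesting little benefit from low to moderate activity. This stands. At a shared gain of 0.02 to 0.05 SD the paired test is favourable in only 3.2 to 5.9% of trials, so the upper rows of the table are hypothetical. The rise to about 6% in Step 4 needs no shared gain.

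Third, most of that rise comes from the two legitimate between-arm tests rather than the paired test, as Step 4 shows. This is correct. It means that setting the paired test aside is not enough: one of the two between-arm tests must also be chosen in advance.

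**Conclusion.** The concern holds and must be fixed, because it determines what result would confirm the primary aim. The textual finding rests on no assumption: hypothesis i has no comparator, no RH-PAT comparison is designated, and one of those listed cannot isolate stimulation.

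The size is conditional. With 40 per arm and two-sided 5% tests, free choice among the three continuous tests raises the favourable false-positive rate from 2.5% to about 6% even when nothing changes. If the arms share a gain, reliance on the EMS-arm paired test adds to this, from a few per cent for a very small gain to 18 to 36% at 0.2 SD, over correlations of 0.3 to 0.7. The shared gain and the correlation are assumptions. The normal/abnormal versions were not counted and would add further opportunities.

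**What to change.** - Reword hypothesis i as a between-arm statement: RH-PAT at 16 weeks is higher with EMS plus exercise than with sham plus exercise.
- Name one primary test at two-sided 5%: the between-arm difference in continuous 16-week RH-PAT, adjusted for baseline RH-PAT. Naming the already planned between-arm t-test on change would also cure the defect; adjustment is preferred only for precision.
- State how the intended matching on age and sex enters that analysis.
- Label the paired and McNemar tests, the normal/abnormal versions and the other between-arm comparison as supportive or descriptive. State that no efficacy claim will rest on a within-arm p-value, or on significance in one arm and not the other.
- Use the same between-arm wording for the secondary efficacy hypotheses. The creatine kinase hypothesis ("No significant difference in blood levels of creatinine kinase across time") asks a longitudinal question and can stay as one.

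The cost is protocol and SAP wording; the measurements needed are already planned. The sponsor gives up the easier within-arm route to a positive result and must accept the sensitivity in Step 5: 80% power only for differences of about 0.45 to 0.61 SD of RH-PAT with adjustment, or 0.49 to 0.75 SD with the change test.

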Peripheral Endothelial Function: Endothelial function will be measured via the RH-PAT index as previously described (6-9). The studies will be performed in a designated quiet, temperature controlled and uniformly lit room. Individuals in the interventional and control groups will be tested at baseline, and will undergo re-testing after completing 16-weeks of training within their assigned arm (within 2 weeks of completion). Subjects will be fasting for 4 hours before the study and will abstain from coffee or tobacco use on the day of the examination. Subjects taking any vasoactive medications, including calcium channel blockers, nitrates, ACE-inhibitors or beta blockers, will discontinue these for 24 hours prior to testing. The study will be conducted in the sitting position in a comfortable chair with armrests. A fitted blood pressure cuff will be placed on one arm, and the finger cuffs of the Endo-PAT 2000 device (Itamar Medical Inc. Ltd., Caesarea, Israel) will be placed on one finger of each hand (10). Subjects will relax for 10 minutes before initiation of the protocol. Baseline blood pressure and heart rate will be obtained via a digital automated blood pressure cuff (Omrom Healthcare, Inc., Vernon Hills, Illinois). The EndoPAT 2000 will be used specifically in this study because it is a Food and Drug Administration–approved noninvasive device, it allows continuous recording of the signal, and interpretation of the data is operator independent. The use of a control arm will allow the elimination of systemic interference of the test and independence from the participant’s knowledge or conscious control of the signals (10-14). The finger probes consist of inflatable latex air cuffs connected by pneumatic tubes to an inflating device controlled through a computer algorithm. A constant counter pressure

(predetermined by baseline diastolic blood pressure) will be applied through the air cushions. This prevents venous pooling and thereby venoarteriolar reflex vasoconstriction while not occluding arterial blood flow. Pulsatile volume changes of the distal digit induce pressure alterations in the finger cuff, which are sensed by pressure transducers and transmitted to and recorded by the Endo-PAT device. A decrease in the arterial blood volume in the distal fingertip causes a decrease in pulsatile arterial column changes, reflected as a decrease in the measured PAT signal, and vice versa.

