Previous studies have demonstrated dependence of the RH-PAT score on nitric oxide, confirming that reported RH-PAT scores indeed reflect changes in nitric oxide– dependent endothelial function, rather than neurohormonal activation (15). The reactive hyperemia protocol will consist of a 16-minute reactive hyperemia test, in the following sequence. A five-minute baseline measurement, after which a blood pressure cuff on the test arm will be inflated to 60 mmHg above baseline systolic blood pressure, or at least 200 mmHg for five minutes (occlusion of pulsatile arterial flow will be confirmed by the reduction of the PAT tracing to zero) after which, the cuff will be deflated, and the post-deflation PAT tracing will be recorded for an additional six minutes. The ratio of the PAT signal after cuff release compared to baseline will be calculated through a computer algorithm automatically normalizing for baseline signal, and indexed to the contralateral arm. The calculated ratio reflects the RH-PAT score (scores below 1.7 will be considered consistent with abnormal peripheral endothelial function).

Although RH-PAT scores may not be the gold standard for endothelial function, several studies have shown good correlation between these methods and more widely accepted methods of

endothelial function testing, such as intra-arterial acetylcholine infusion and brachial artery Doppler ultrasound following reactive hyperemia (11, 13, 14).

Laboratory Testing: Laboratory testing will be undertaken in all participants at baseline, and at 16-weeks follow-up in both the intervention and control group. Venous blood will be drawn for high-sensitivity CRP, uric acid, fasting glucose, HbA1c, lipid panel, lipoprotein A, homocysteine and fibrinogen. For patients in both groups, venous blood will also be tested for creatinine kinase levels at baseline, 8-weeks (halfway into the training programs), and 16-weeks (after completing each respective training program for both groups). A blood sample of approximately 30 mL will be drawn and all samples will be sent to the Mayo Clinic central laboratory for analysis.

Body Weight, Height, and Waist Circumference: Body height, weight and waist circumference will be measured using calibrated devices. Body mass index will be calculated as mass (kg)/height (m²).

VO2 MAX and Maximal Heart Rate: This will be tested using exercise treadmill testing in the conventional manner.

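### For continuous outcomes, including RH-PAT for the primary aim, the arms are compared at follow-up by two unadjusted t-tests with neither named as primary; one prespecified baseline-adjusted ANCOVA would settle the choice and usually gain precision

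*Combined protocol and SAP*

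**What the plan says.** The Primary Aim is the effect of training "on peripheral endothelial function as measured using EndoPAT". Under Outcomes and Measurements, Peripheral Endothelial Function, both arms are measured twice: "Individuals in the interventional and control groups will be tested at baseline, and will undergo re-testing after completing 16-weeks of training". The same section defines the measure as a ratio ("The calculated ratio reflects the RH-PAT score") and sets 1.7 as the cut-off for an abnormal score.

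Trial Design says the study "will include 80 healthy individuals who are employees at Mayo Clinic, Rochester MN". Statistical Analysis plans "a control group into which individuals will be randomly assigned in a 1:1 ratio" and adds "We will match individuals, a priori, as best as possible on age (within 5 years) and sex", without saying how the matching is done.

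The same section plans two between-arm analyses of follow-up data:

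- **Values:** "We will compare values of each parameter between groups at baseline and after 16-weeks using unmatched analyses"
- **Change:** "we will compare the differences between baseline and 16-weeks follow-up for each parameter between groups using unmatched analyses"

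Each uses Student's t-test for continuous variables and a chi-squared test for normal/abnormal categories. Paired t-tests and McNemar's tests are also planned, but within arms. No section names a primary test, a covariate or a baseline-adjusted model. No alpha, power, effect size, SD, correlation or sample-size rationale is given.

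**The concern.** The t-test on 16-week values ignores the baseline measurement. The t-test on change uses it, but fixes the baseline slope at 1. ANCOVA estimates the slope from the data. Which t-test is the more precise depends on the correlation between the two visits, and the documents do not give it.

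Two things are at stake. First, precision: with 80 people, the choice of analysis can matter as much as a sizeable change in sample size. Second, designation: the two tests can give different answers on the same data, and nothing written beforehand says which one answers the primary aim.

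**Working it through.** **Inputs.** From the documents: 80 participants at 1:1, so n = 40 per arm and N = 80. Assumed, because the documents are silent: two-sided 5%, no dropout, equal SDs at both visits, effect 0.5 SD, correlation r = 0.3, 0.5, 0.7 or 0.8. There is no sample-size calculation in the plan to reproduce.

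**Variance of the arm difference, relative to the t-test on 16-week values**

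- 16-week values: 1
- Change: 2(1 − r)
- ANCOVA with k covariates: (1 − r²)F, where F = (N − 3)/(N − 3 − k) is the cost of estimating k slopes. F = 77/76 for baseline only. F = 77/74 for baseline, age and sex, with age and sex assumed to explain nothing.

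**Where ANCOVA has the smaller standard error**

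- Against 16-week values it needs r > √(1 − 1/F). This is √(1/77) = 0.114 for one covariate and √(3/77) = 0.197 for three.
- Against change it needs r < 2/F − 1. This is 152/77 − 1 = 0.974 for one covariate and 148/77 − 1 = 0.922 for three.

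The ranges are therefore about 0.11 to 0.97 (baseline only) and about 0.20 to 0.92 (three covariates). A simulation of the baseline-only model agreed with the variance formula: at r = 0.15 the relative variances for 16-week values, change and ANCOVA were 0.997, 1.691 and 0.988.

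**Largest loss outside the range.** This is √F: √(77/76) = 1.007 and √(77/74) = 1.020, or 0.7% and 2.0% in standard error. With an assumed 20% dropout (32 per arm, N = 64) it is √(61/60) = 1.008 and √(61/58) = 1.026, or 0.8% and 2.6%.

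**Power at 0.5 SD.** Noncentral t, with SE₀ = √(2/40) = 0.2236 SD multiplied by the square root of the relative variance. Degrees of freedom are 78 for the t-tests, 77 for baseline-only ANCOVA and 75 for three covariates.

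| Analysis | r = 0.3 | 0.5 | 0.7 | 0.8 |
|---|---|---|---|---|
| 16-week values | 59.8% | 59.8% | 59.8% | 59.8% |
| Change | 46.3% | 59.8% | 81.4% | 93.7% |
| ANCOVA, baseline only | 63.3% | 71.7% | 86.7% | 95.5% |
| ANCOVA, three covariates | 62.1% | 70.5% | 85.8% | 95.0% |
| Three covariates minus better t-test (points) | 2.3 | 10.7 | 4.4 | 1.3 |
| Three covariates minus worse t-test (points) | 15.8 | 10.7 | 26.0 | 35.2 |

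At 32 per arm and r = 0.5, power is 50% for either t-test and 60% for three-covariate ANCOVA.

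**Unequal SDs.** Let the 16-week SD be c times the baseline SD. In units of the 16-week variance, the change test then has relative variance (c² + 1 − 2rc)/c². For c = 1.25 the relative standard errors, change against three-covariate ANCOVA, are 0.721 and 0.729 at r = 0.7, and 0.600 and 0.612 at r = 0.8. Power is 86.5% against 85.8%, and 95.7% against 95.0%. The change test is slightly ahead because the true slope rc is near 1 (0.875 and 1.0). Baseline-only ANCOVA is marginally behind change for r of about 0.72 to 0.86.

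**Disagreement of the two planned t-tests.** This is a separate matter from precision. In simulation at 0.5 SD they differ on p < 0.05 in 32 / 32 / 35 / 38% of trials at the four correlations. With no effect, at least one is significant in 8.9 / 9.2 / 9.5 / 9.5%.

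**The case against.** The strongest reply is that the plan already contains the change test, which is valid and uses baseline. Simply naming it as primary would cure the ambiguity, and it fits a hypothesis worded as improvement. Against the better of the two t-tests, ANCOVA gains little except near a correlation of 0.5; the large gains are against the worse one and count only if the team would have relied on it. Adding age and sex costs a little power when they are uninformative (71.7% to 70.5% at correlation 0.5). All of this stands. It makes the ANCOVA part an efficiency recommendation, while the need to name one analysis stands whatever the gain.

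A reader might infer more than the documents support:

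- **That the planned tests are biased or invalid.** Under randomisation neither is.
- **That ANCOVA always wins, or that one correlation range fits every ANCOVA.** The range depends on the number of covariates, the sample size and equal SDs. With a 16-week SD 1.25 times baseline, the change test can be slightly ahead at correlations inside both ranges.
- **That the arms are compared only by t-tests.** Chi-squared tests of normal/abnormal categories are also planned; this point concerns the continuous comparisons.
- **That the team cannot know the correlation.** The documents do not state it. That does not show that the team lacks it.
- **That matching makes the unmatched tests wrong.** No mechanism is given. Only if matching constrains allocation would the unmatched standard error be too large, and then only as far as age and sex predict the outcome.

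**Conclusion.** The point holds as a recommended change to the analysis, not as a flaw that invalidates it. The firmer half is that no primary between-arm analysis of RH-PAT is designated, although two follow-up t-tests are planned that can disagree.

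The other half is precision. The case for ANCOVA is mainly insurance. With equal SDs its worst loss to the better t-test is under 1% in standard error with baseline alone, and 2.0% to 2.6% with three covariates at 40 to 32 per arm. Its gain over the better test peaks near a correlation of 0.5, at about 11 to 12 power points, and is about 1 to 5 points at the other correlations tabulated. These sizes rest on an assumed effect of 0.5 SD and assumed correlations; the gain over the change test can disappear if the SDs differ.

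**What to change.** Before unblinding, name one primary analysis of RH-PAT: an ANCOVA of the 16-week value on arm and baseline RH-PAT. Report the adjusted difference with its 95% CI in place of the two between-arm follow-up t-tests. Fix the analysis scale and a residual check in advance, because RH-PAT is a ratio. Use the same model for the other continuous outcomes measured at both visits, with each scale prespecified (for example log for skewed laboratory markers).

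Age and sex may be added, since the plan says participants are matched on them. The SAP should also state how that matching is done; if it forms allocation strata, include the stratum in the model. The chi-squared comparisons need no change on this account.

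The cost is SAP wording. No new data are needed: baseline RH-PAT is measured, and matching already requires age and sex. Baseline uses one degree of freedom, and age and sex two more.
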